TBS parameters include intermittent TBS of 600-1800 pulses, delivered at up to 120% of motor threshold (based on [63]; and [name] et al., American Journal of Psychiatry under review). We will follow all standard TMS operating procedures, including those regarding rating scales, safety and administration.

Following our standard operating procedures, during TMS sessions Veterans will sit quietly wearing hearing protection and will not interact with study staff unless there are problems related to device positioning, etc. Motor threshold determination may be repeated if clinically warranted. The minimum number of TMS sessions in the acute series will be 15. The treatment series may conclude before #36 if a patient demonstrates two consecutive weeks of remission. Remission and number of sessions required will be determined by checking rating scales following standard clinical procedures (e.g., using the inventory of depressive symptomatology (IDS-SR <15)).

Safety will be assessed at every TMS session by recording spontaneously reported

adverse events. Participants will be queried daily about potential side effects associated with TMS such as headache and dizziness as well as any changes in medications, usage of drugs or alcohol, and mood. We will use a standardized self-report questionnaire (the TMS Daily Screener) to ask these questions. The TMS Daily Screener is administered by TMS staff on a dry- erase sheet without any identifiable information or participant ID. Responses on this screener are used to determine participant safety for daily TMS procedures, are not recorded/saved as

part of study data collection, and are erased at the end of the TMS session. If any reported

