changes indicate that TMS administration may be unsafe, the session may be rescheduled. If reported changes are significant e.g., previously unreported consumption of illicit drugs that contraindicate TMS administration (i.e., render administration unsafe), the participant may be removed from the treatment part of the study. Participants discontinued from treatment may still be eligible for follow-ups associated with the MRI component of the study and will be asked if they wish to continue with that portion of the study. Following standard TMS operating procedures, a TMS technician will monitor participants for treatment-emergent safety issues such as seizures. Side effects will be coded using the current version of the Medical Dictionary for Regulatory Activities, following procedures used in prior TMS studies [64,65]. As described above, participants will be required to wear hearing protection during TMS. Reflecting the at- risk nature of the Veteran participants, a licensed physician with experience with neuromodulation and suicidality will always be available during study procedures.

D4.4.1a Considerations regarding pregnancy

TMS has been safely used on pregnant women, (e.g., [6]), but it is not FDA cleared for use in this population. We will utilize standard practices for investigational device and investigational TMS research (e.g., [25]). As noted above, pregnancy/lactation, planning to become pregnant during the study, or those who do not agree to consistently use a measure birth control during the study are excluded. Pregnancy tests are administered as part of standard clinical procedures during hospitalization. We will administer pregnancy tests to women identified in outpatient settings to verify safety for TMS/MRI.

Participants will be asked to inform study personnel if they become pregnant; participants may also be asked to receive a urine pregnancy test if situations emerge where there is a possibility of pregnancy. Prior to the administration of each TMS session participants will be asked about any changes in medications, this includes birth control use. Participants will re-affirm continued use of their designated choice of birth control. Because pregnancy is an exclusion criterion, if they become pregnant during the study they will be removed from participation and managed following best clinical practices.

D4.4.1b TMS Assignments [active VS sham]:

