The potential benefits of identifying effective treatments for suicidal patients appear to outweigh the potential risks of this study. Both BCBT and TMS alone have been found to reduce suicidal ideation and we believe that participants in both conditions will experience significant improvement in symptoms. Improvements in assessment and treatment of suicidal patients are urgently needed. The major risk, that of adverse events, should not be increased by study participation and in fact should be reduced by the enhanced monitoring and risk reduction procedures noted above. If neuroimaging biomarkers are clinically useful, participants may gain access to related technology that may help them self-monitor their suicidal risk at a later date.

Any incidental neurological information gained during scanning of the brain may be of potential benefit to subject and the subject's physician.

G4. Importance of the Knowledge to be Gained

Suicidal behavior is a significant public health issue and of critical importance to Veterans. The evaluation of interventions to reduce suicidal behavior may have important benefits for multiple aspects of society. Additionally, this study will advance our understanding of the neurobiology of suicidality. These findings can be used to develop neurobiology-based clinical criteria for identifying Veterans at elevated risk for suicide.

Importantly, these objective measures are less susceptible to the reliability issues that affect the accuracy of self-report measures. Knowledge gained will be fundamental for the development of targeted therapeutic interventions that can modulate neural function in regions implicated in suicide. Thus, our results will have important implications for a variety of stakeholders, including patients, family members, healthcare providers, managed care organizations, health insurers, administrators, and policy makers.

G5. Data and Safety Monitoring Plan

Weekly meetings with study staff and study investigators will be held to review progress with regard to enrollment, any adverse events, and attrition/noncompliance. Circumstances surrounding any identified adverse events, incidents of subject dissatisfaction, or subject noncompliance/withdrawal of consent will be tracked regularly and discussed. Adverse events tracking files will be routinely updated. If data patterns consistent with any safety issues are suggested, the principal investigator will seek consultation with, and peer review by, other

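### Side-effect answers collected on a standardized screener at every TMS session are erased and no other solicited side-effect measure is kept, so common non-serious effects are likely to be under-captured

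*Combined protocol and SAP*

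**What the plan says.** D4.4.1 (TMS Procedures) describes two routes for safety information at a TMS session.

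- **Recorded route.** "Safety will be assessed at every TMS session by recording spontaneously reported" adverse events.
- **Prompted route.** "Participants will be queried daily about potential side effects associated with TMS such as headache and dizziness", and also about medication changes, drug or alcohol use, and mood. "We will use a standardized self-report questionnaire (the TMS Daily Screener) to ask these questions".

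The prompted answers go on a dry-"erase sheet without any identifiable information or participant ID". Their fate is stated in one sentence, which the PDF splits over a line break: "Responses on this screener are used to determine participant safety for daily TMS procedures, are not recorded/saved as" and then "part of study data collection, and are erased at the end of the TMS session".

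Further on, D4.4.1 says "Side effects will be coded using the current version of the Medical Dictionary for Regulatory Activities", without naming the record that supplies the side effects. E1.1 allows for adverse-event analyses among the preliminary analyses. G5 provides for weekly safety review and says "Adverse events tracking files will be routinely updated". Table 2, the assessment battery, contains no TMS side-effect scale at any visit.

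**The concern.** Prompted and volunteered reports are different measurements. A participant who says yes when asked about headache has answered a question. Under D4.4.1 that answer belongs to the screener, not to the spontaneous reports that are recorded. The effects most exposed are the ones the plan itself expects: B4.1 names treatment-site discomfort as the most common, G2.7.1 lists headache and local pain, and the screener asks about headache and dizziness. These are rarely serious, so serious-event reporting will not pick them up.

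At stake is the tolerability record of a sham-controlled device trial. The plan already gathers structured side-effect data at each session and then discards it, and it cannot be rebuilt later. Answers on the same sheet can also lead to a session being rescheduled or to removal from treatment, and the text requires no stored record of the answer behind that decision.

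**Working it through.** The plan gives no side-effect rate, no capture fraction and no safety power, so there is no figure of its own to reproduce. The check is mainly a reading of the passages side by side.

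**1. What is kept and what is not**

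| Information | Per-session screener | Kept elsewhere |
|---|---|---|
| Prompted non-serious side effects | Asked, then erased | No retained measure named |
| Volunteered adverse events | – | Recorded at each session (D4.4.1) |
| Events seen by staff | – | Technician monitoring (D4.4.1); adverse-event tracking files (G5) |
| Serious adverse events | – | Recorded and reported to IRB and DSMB (G2.7.3) |
| Mood and ideation | Mood asked, then erased | IDS-SR and PCL-5 weekly; Scale for Suicide Ideation at the weekly BCBT visits (Table 2) |
| Substance use | Asked, then erased | AUDIT and DUDIT at baseline, endpoint and follow-up (Table 2) |
| Medication changes | Asked, then erased | Monthly chart extraction (D5, D5.1) |

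Only the first row has no retained counterpart. For mood, substance use and medication, what is lost is session-level detail.

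**2. Volume of erased records**

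Inputs: 130 randomized, about 65 per arm (E1); 15 to 36 TMS visits each (D4.4).

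- Lower: 130 × 15 = 1,950 (65 × 15 = 975 per arm)
- Upper: 130 × 36 = 4,680 (65 × 36 = 2,340 per arm)

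This assumes that all 130 complete the stated range. Dropout would lower it. It counts forms and does not measure bias.

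**3. Direction of the effect (illustration on assumed rates)**

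Let c be the share of prompted side effects that are also volunteered, taken as equal in both arms. Observed rates are then c·p for active and c·q for sham, and the observed difference is Δ = c(p − q). With n = 65 per arm and two-sided alpha 0.05,

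Power = Φ[(Δ − 1.96·SE0)/SE1], where SE0 uses the pooled rate and SE1 the two separate rates.

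Example: p = 40%, q = 20%, c = 0.5. Observed rates are 20% and 10%, Δ = 0.10, SE0 = √(2 × 0.15 × 0.85/65) = 0.0626, SE1 = √((0.16 + 0.09)/65) = 0.0620. Power = Φ(−0.367) = 36%.

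| Assumed rates, active vs sham | c = 1.0 | c = 0.75 | c = 0.5 | c = 0.25 |
|---|---|---|---|---|
| 30% vs 15% | 15.0 points, 54% | 11.3, 40% | 7.5, 27% | 3.8, 15% |
| 40% vs 20% | 20 points, 71% | 15, 54% | 10, 36% | 5, 19% |
| 50% vs 25% | 25.0 points, 85% | 18.8, 67% | 12.5, 45% | 6.3, 23% |

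Each cell gives the observed difference and the power. Equal under-capture shrinks both the rates and the difference. If c differed between arms, the difference could move either way. None of p, q or c is in the documents.

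**The case against.** The strongest defense is that the screener is a same-day safety check, made ID-free by design, and that the safety record does not depend on it. Much of this stands, and it rules out several stronger readings.

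- **That the safety record holds only spontaneous reports.** It does not. Technician monitoring, assessment before and after each treatment (G2.7.1), serious-event recording and the tracking files also feed it.
- **That every prompted answer is lost.** The plan neither states nor rules out that staff copy a positive answer to the adverse-event file before wiping the sheet. It promises MedDRA coding of side effects, so some must be written down, and it relies on standard TMS operating procedures that are not among the documents. Total loss is an inference.
- **That mood, medication and substance-use information is lost.** These are retained on the schedules in the table above. For suicidality, a weekly scale is better outcome data than an unscored daily question.
- **That a planned comparison of side effects between arms is compromised.** No hypothesis and no Aim 1 analysis makes one. E1.1 says only that adverse-event analyses may be included.

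There is also a fair confidentiality argument against storing routine drug-use answers under a study ID at each session.

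The defense does not reach the side-effect items. The text sets a rule that their answers are not study data and are erased, records volunteered events instead, and names no other solicited source. A site that follows the plan literally has no solicited non-serious events to code.

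**Conclusion.** The point holds as an inexpensive improvement to safety data collection. As written, the plan keeps no solicited measure of non-serious TMS side effects, so effects admitted only on questioning are likely to be under-captured in the MedDRA-coded data and in any adverse-event analysis. Between 1,950 and 4,680 completed screeners would be wiped if all 130 Veterans complete 15 to 36 sessions. The proportion of side effects lost is unknown.

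The conclusion assumes that some participants who report a mild effect when asked would not volunteer it, and that positive answers are not copied elsewhere by a procedure outside the documents. If they are copied, the fault is in the wording and the plan should say so. The primary and secondary efficacy analyses do not depend on this point.

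**What to change.** In D4.4.1, replace the erase rule for the side-effect items:

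1. Before the sheet is wiped, TMS staff enter each positive side-effect answer, with study ID and date, in a short adverse-event form in VA REDCap, which the study already uses (F7.1). The entry should be made by the TMS provider, whom D4.5.1 describes as blind, and not by the un-blinded member who sets up the coil.
2. Any screener answer that leads to a rescheduled session or to removal from treatment is entered as the reason for that decision.
3. The form is named as the source for MedDRA coding, alongside the spontaneous reports.
4. Solicited and spontaneous events are reported separately by arm.

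Routine per-session substance-use answers need not be stored, which avoids the confidentiality problem.

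The cost is one short form and a brief entry per positive answer, by staff already present and already asking the question. Reported side-effect rates will be higher than under spontaneous reporting alone, so the two sources should not be pooled without labels.

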D5.2 EHR variable construction: EHR measures are listed in Table 5. Monthly EHR sums will be averaged by quarter and by year. If categorical variables change over an aggregated time point, the most consistent designation over the analyzed epoch will be used.

Health Services Utilization
Outpatient Visits (any service)
Outpatient Visits (MH service)
Emergency or Urgent Care Visits
Inpatient MH
Inpatient (any service)
Pharmaceutical Utilization
Antidepressant
Antipsychotic
Mood Stabilizer
Anxiolytics
Other medications (non-psychiatric)
Change in Pharmaceutical
Antidepressant
Antipsychotic
Mood Stabilizer
Anxiolytics
Other medications (non-psychiatric)
Mental Health (Current and Lifetime)
Depression
Bipolar disorder
Schizophrenia or schizoaffective disorder
Generalized Anxiety Disorder
Posttraumatic Stress Disorder
Specific Phobia
Panic Disorder
Social Phobia
Personality Disorder
ADHD
SUD
Gambling Disorder
Eating Disorders
Suicidality

Table 5. EHR data extracted at baseline and follow-

E. DATA ANALYSIS

E1. Design and Sample Size

This is a single-site, two-arm RCT with individual participant urn randomization. We propose to randomize 130 Veterans. Approximately 65 will be randomized to active TMS+BCBT and 65 participants will be randomized to sham TMS+BCBT. Recruitment for the intervention will cease once randomization goals are met (i.e. n= ~65 Veterans per condition). Additionally, we will be enrolling 60 Veterans, who will be matched on age (within 5 years), primary psychiatric diagnosis, and sex, for a total of 190 Veterans to be enrolled. A subsample of these veterans (120 in total; one group (n=30) with suicide ideation and another group (n=30) with suicide attempts; and controls (n=60) will be used in the analyses of brain-based biomarkers for suicidality. Veterans will be assessed at the study timepoints outlined in C3. Assessments.

E1.1 Overall Analytic Approach across Aims

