Preliminary analyses will include descriptive statistics to examine the distributional and psychometric properties of the variables (e.g., normality, internal consistency). Variables will be transformed to achieve normality if necessary. We will also examine post-inclusion attrition by comparing study completers to dropouts on sociodemographic, baseline, and length of admission data to determine if they differ systematically. Preliminary analyses may also include analyses of adverse events, progress of recruitment and retention, and quality markers as the study progresses. In keeping with the intention to treat principle, missing data will be handled with multiple imputations (m=20) with assumptions checked with sensitivity analyses [43,44] [32]. Our main analysis will not adjust for covariates other than baseline value of the outcome and design factors (balancing factors used in the urn randomization procedure) under the assumption that randomization produced groups balanced on measured and unmeasured confounders. Additionally, the data from this study across all Aims will be combined with data from subjects who completed neuroimaging procedures in PVAMC IRB protocol #2018-051.

Data from this study, across all Aims, will also be combined with data from subjects who completed procedures for PVAMC IRB protocol #IRB-2020-008. Data from this study related to recorded interviews, de-identified with the exception of assessment dates, will also be shared with the PVAMC research study “Longitudinal Assessment of the Sleep-Suicide Link in Veterans Discharged from Inpatient Psychiatric Care” (IRB-2020-008), for training of staff and inter-rater reliability analysis (i.e., to calculate agreement across interviewers and to make final decisions on ratings).

E2. Aim 1 Analytical Plan (Analyses Related to Treatment)

The data from this study for Aim 1 may be combined with data from subjects who completed neuroimaging procedures in PVAMC IRB protocol #2018-051. Data from this study, for Aim 1 may also be combined with data from subjects who completed procedures for PVAMC IRB protocol #IRB-2020-008.

E2.1 Interim analysis and early stopping of treatment

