E2.4.1 Statistical power and sample size considerations: As we view tertiary analyses as exploratory and hypothesis generating, we do not present a priori specified sample size or minimum detectable effect size statistics. We have no doubt that we may be underpowered to detect all but large moderation effects. Our inferences will be made cautiously and be guided

by confidence intervals obtained by bootstrap resampling of the observed data.

E3. Aim 2 Analytical Plan (Analyses Related to Cognition and Neuroimaging)

All de-identified data from this study for Aim 2 will be combined with data from subjects who completed neuroimaging procedures in PVAMC IRB protocol #2018-051.

E3.1 Evaluate the relationship between STBs and reward circuits involved in decision-making in Veterans.

Hypothesis: Neural and behavioral correlates of decision-making will differentiate Veterans with STBs from those without STBs.

Rationale: Suicidality is associated with maladaptive decision-making. Neuroimaging in non-Veterans has shown that STBs are accompanied by functional and anatomical differences in the striatal-to-VMPFC reward circuit implicated in decision-making. It is unknown if these potential neurocognitive markers of suicide generalize to Veterans.

Between-group contrasts of decision-making, structural MRI, and functional MRI will be used to test our hypothesis.

E5.1 Participant groups: The STB group will be comprised of Veterans hospitalized for suicide attempt (up to n=30) or suicidal ideation (up to n=30). The diagnosis matched control group is comprised of Veterans (up to n=60) without current STBs. Per power estimations computed with G Power software⁴², 85% power to detect a medium-sized effect of group (0.4) in an ANCOVA model with three groups and two covariates is afforded by a total sample size of 72, or n=24 participants per group. Our enrollment targets exceed this estimate to account for loss of participants that are unable to complete all aspects of the study.

Data sources: Decision-making tasks include the scanned reward expectancy task (card guessing), and the un-scanned Iowa Gambling and Monetary Choice (Delay Discounting) tasks. Structural MRI and diffusion MRI data. FMRI data used in Aim 1 analyses will come from either the card guessing reward task or resting state functional MRI runs.

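### The stopping rules can end C-SSRS outcome assessment for randomised Veterans, and the pooling text does not confine the active-versus-sham analyses to those randomised

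*Combined protocol and SAP*

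**What the plan says.** On stopping and follow-up:

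- D4.4.1 (TMS Procedures): a Veteran for whom TMS has become unsafe may be taken out of the treatment part. Such Veterans may keep access to the imaging component's follow-ups and are asked whether they want that.
- D4.4.1a: a Veteran who becomes pregnant is taken out of participation. No outcome follow-up is mentioned.
- D4.4.3: the PI reviews attendance and may discontinue a Veteran from the study before the intervention period ends. The only stated consequence is that the mental health provider is told.
- D4.5 (Follow-Up Visits): visits count from the start of the intervention, at 6 and 12 months for TMS+BCBT-only Veterans and at 6, 12 and 24 months for those also in imaging. G2.6 says that all participants are assessed at sessions after treatment. Neither mentions Veterans who stopped early.
- 3-month endpoint: the Introduction and the D4 visit table place it at the last therapy session. The Table 2 footnote and D4.5 (Intervention Endpoint Visit) place it at the 12th therapy visit and at 12 weeks, as if these were one date.
- E1.1 on missing data: "In keeping with the intention to treat principle, missing data will be handled with multiple imputations (m=20) with assumptions checked with sensitivity analyses".

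On the analysis set:

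- E1: "This is a single-site, two-arm RCT with individual participant urn randomization".
- E1.1: "the data from this study across all Aims will be combined with data from subjects who completed neuroimaging procedures" (protocol 2018-051), and "Data from this study, across all Aims, will also be combined with data from subjects who completed procedures for PVAMC IRB protocol #IRB-2020-008".
- E2, headed as the treatment analyses, changes *will* to *may* for both protocols: "Data from this study, for Aim 1 may also be combined with data from subjects who completed procedures for PVAMC IRB protocol #IRB-2020-008".
- E3: "All de-identified data from this study for Aim 2 will be combined with data from subjects who completed neuroimaging procedures", naming 2018-051 only.

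**The concern.** An intention-to-treat comparison needs outcomes on everyone randomised, whether or not they finished treatment. If staff follow D4.4.1, D4.4.1a and D4.4.3 literally, some Veterans who could still be interviewed will not be. Two of the stated reasons, poor attendance and unsafe substance use, could plausibly be related to suicide risk, so the missing outcomes may be informative. Imputation then has to stand in for data that could have been collected.

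The 3-month assessment is especially exposed. E2.2 states that the main hypothesis is an immediate effect of TMS, and the endpoint visit is the one whose date depends on therapy attendance.

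The second issue is smaller. Subjects from another protocol have no random assignment here. Text that allows or requires them in the treatment aim leaves the analysis set undefined at the point where a randomised trial should be most explicit.

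**Working it through.** **Step 1. What happens to each kind of stopper.**

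| Reason | Restrictive text | Text that could keep the Veteran in assessment |
|---|---|---|
| TMS unsafe | D4.4.1: out of the treatment part; optional imaging follow-ups | D4.5 schedule; G2.6 |
| Pregnancy | D4.4.1a: out of participation | D4.5 schedule; G2.6 |
| Poor TMS attendance | D4.4.3: out of the study; provider told | D4.5 schedule; G2.6 |

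In each row the general statements do not say that they override the specific one. The plan does separate components elsewhere: under D4.3.1 a failed drug screen ends imaging but not treatment. No matching rule says that ending treatment leaves outcome assessment in place.

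**Step 2. What the imaging route covers.** E2.2 names 3, 6 and 12 months. Imaging follow-ups fall at 6, 12 and 24 months, with the C-SSRS at each (Table 2). That reaches 2 of the 3 named time points and misses 3 months. It is not available to a Veteran who is not in imaging.

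**Step 3. The endpoint anchors.** Two invented cases, assuming weekly therapy:

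| Case | Last session | 12th visit | 12 weeks from start |
|---|---|---|---|
| Stops after session 5 | week 5 | never | week 12 |
| Misses 3 weeks, then completes | week 12 + 3 = 15 | week 15 | week 12 |

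The three anchors agree only for a Veteran who attends every week.

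**Step 4. What other sources recover.** Suicide deaths come from medical and death records (E2.2). Utilisation comes from chart review (Table 2), and health-record data are extracted at 6, 12 and 24 months (D5). None of these is the C-SSRS interview from which E2.2 takes its counts of attempts, aborted attempts and interrupted attempts.

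**Step 5. The plan's own figure.** E2.2.1 uses d = sqrt(16/n) with n = 65 per arm: sqrt(16/65) = 0.496, stated as 0.50. This reproduces. The formula takes all 65 as observed. If an assumed 10%, 20% or 30% of outcomes were missing in each arm for any reason, complete-case n would be 58.5, 52 or 45.5 and d would be sqrt(16/58.5) = 0.523, sqrt(16/52) = 0.555 or sqrt(16/45.5) = 0.593. These rates are assumptions. The figures describe precision only; they do not measure bias or the loss that these rules would cause.

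**Step 6. The pooling text.** E1.1 (all Aims, *will*, both protocols), E2 (Aim 1, *may*, both protocols) and E3 (Aim 2, *will*, one protocol) cannot all be the rule. E1.1 gives training and inter-rater use of interviews a separate sentence, so those uses do not explain the word combined. The E2.2 model needs random assignment and the urn factors, and no passage says how a subject without an assignment would enter.

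**The case against.** The strongest reply on follow-up is that D4.5 schedules the 6- and 12-month visits without making them conditional on completing treatment, offers telephone contact and pays for visits to limit attrition, and that G2.6 covers all participants. D4.4.1 removes a Veteran only from treatment, so its imaging sentence may add an option rather than cancel the other visits. Much of this stands. A reader might infer that TMS+BCBT-only Veterans have no follow-up rule at all; the documents do not support that. But D4.4.3 speaks of leaving the study and D4.4.1a of leaving participation, both wider than leaving treatment, and nothing says which text prevails.

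On pooling, the reply is that an outside subject has no value on the model's main exposure, so E2.2 already implies a randomised-only comparison. That also stands. A reader might infer a plan to enlarge the sham arm with outside subjects; no passage says so. The label is ambiguous too, since E3.1 uses it for imaging: "FMRI data used in Aim 1 analyses will come from either the card guessing reward task or resting state functional MRI runs". The E2 sentences may be carried over from that numbering. This explains the conflict but does not remove it, because E1.1 covers all Aims and E2 is headed as treatment analysis.

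A reader might also try to count those without an imaging route by setting E1's 30 + 30 imaging Veterans ("A subsample of these veterans (120 in total; one group (n=30) with suicide ideation and another group (n=30) with suicide attempts") against 130, giving 130 - 60 = 70. E1 describes an analysis subsample, not a cap on scanning. D2.2 expects about 20% of potential participants to have an MRI contraindication; if that alone kept Veterans out of imaging, the count would be 0.20 × 130 = 26. D4.5 also allows imaging-only Veterans, which moves the count the other way. The number is not determined.

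Finally, nothing shows that losses would differ by arm.

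**Conclusion.** The point holds and should be fixed, with follow-up after stopping as the main part. The stated discontinuation rules conflict with the general visit schedule and, followed literally, lose C-SSRS outcomes that could be obtained. The 3-month endpoint has three anchors that part for anyone who stops or falls behind. Record-based capture and multiple imputation reduce the damage but do not replace the interview counts.

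The pooling conflict is secondary. It is a missing explicit restriction in a design that otherwise implies one.

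No bias size can be stated: the documents give no discontinuation rate, no number of TMS+BCBT-only Veterans and no number of outside subjects. The stated detectable difference of 0.50 SD at 65 per arm does not change. The conclusion rests on the visible text; consent pages, which might address follow-up after discontinuation, are not in the file.

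**What to change.** 1. Reconcile D4.4.1, D4.4.1a, D4.4.3, D4.5 and G2.6 so that stopping study treatment does not by itself end outcome assessment. Randomised Veterans who have not withdrawn consent are invited to the planned C-SSRS assessments at 12 weeks, 6 months and 12 months, by telephone if needed. Anchor the 3-month assessment to the calendar (12 weeks from start) in the Introduction, the D4 table, the Table 2 footnote and D4.5. The rules for when treatment stops stay as they are.
2. State in E2 that the active-versus-sham analyses in E2.1 to E2.3 include all and only Veterans randomised in this trial, as assigned. Limit pooling with the two other protocols to Aim 2 and other non-comparative work, align *will* and *may* across E1.1, E2 and E3, and clear up the use of Aim 1 in E3.1.

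The cost is protocol and SAP wording plus some added tracking. The visits, the telephone option and the $50 payments (3 × $50 = $150 per Veteran for the three assessments) are already in the plan.
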